#### 11.2.3 Rescue Therapy

If subjects are shown to be either newly or persistently infected with confirmed scabies mites by RCM on or at any time from Day 14, standard of care may be offered. Rescue therapy may not be offered in the absence of scabies mites or based on symptomology only.

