  - a. Where rescue medication has been taken (identified on the concomitant medications page of the eCRF), any mite death occurring after the start date of rescue medication will be ignored and the mite will continue to be considered alive. If the mite has already died prior to or on the start date of rescue medication, it will be considered dead for all subsequent visits as stated here.

3. Should the RCM responses indicate a status of 'live' at an assessment occurring after an assessment with a status of 'dead', this will be assumed to be a new infection and thus ignored, i.e. the mite identified at Baseline will still be assumed to have died. This will therefore not impact the analysis of the primary efficacy endpoints.
4. Where data are missing for any of the responses required to determine the status of a mite and therefore the mite status cannot be established, the status of the mite will be assumed not to have changed from the previous non-missing assessment (i.e. the last observation will be carried forward). This includes where a subject withdraws early, in which case the last observation will be carried forward for all remaining visits. Where the last observation is carried forward, this will still be subject to the above rules 1 to 3.

These imputation methods will be applied to all missing adult mite assessments, regardless of the number of lesions for which data are missing for a subject at a timepoint. If data are missing at the subject level (i.e. the RCM assessment is not completed for any lesion at a timepoint for a subject), all mites being evaluated will have their status imputed and therefore no subjects will be missing in the primary analysis summaries presented at each post-Baseline visit.

It should be noted that the above rules may not be exhaustive. If any ambiguity remains in the status of the mite after applying these rules, subject data will be reviewed on a case-by-case basis prior to breaking the blind.

All analyses of the dead/alive response described in the SAP for the primary endpoints will use the values obtained after applying the strategies for any imputation where there is ambiguity or missing data. Similarly references to 'first/last time point where dead/alive' refer to the first/last occurrence once these imputations have been applied. Following review of these analyses, post hoc sensitivity analyses may be considered to assess the impact of these imputations, as described in [Section 6.10.1.6](#).

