#### **6.10.3 Exploratory Endpoints**

All exploratory endpoints will be analyzed and summarized using the PPAS as the primary analysis set. Per [Section 6.4](#), selected exploratory endpoints may be repeated on the FAS post-hoc if deemed worthwhile to assess any impact to the conclusions made. Where this is the case, the following endpoints will be repeated:

- Presence and number of total mites and burrows assessed visually at Days 7, 14 and 28 (see [Section 6.10.3.1](#)).
- Changes in assessment of clinician-reported scabies symptomology (see [Section 6.10.3.2](#)).
- Clinical cure rate (see [Section 6.10.3.4](#)).

The exploratory endpoints will be assessed using descriptive summaries. However, if deemed of interest following review of the summaries, further analyses of these endpoints may be considered post-hoc.

With the exception of clinical cure rate, data are included in all exploratory endpoint summaries irrespective of any exposure to rescue medication. The impact of rescue medication on data used in the summaries for clinical cure rate are detailed further [Section 6.10.3.4](#).

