##### **6.10.3.1 RCM Assessment**

#### **Changes in Adult Mite Motility**

The presence and changes in adult mite motility (movement and peristalsis) over time will be assessed in an exploratory manner using descriptive summaries, and with the adult scabies mite as the unit of analysis.

The proportion of adult mites with and without movement respectively will be calculated at each RCM time point as the total number of adult scabies mites with and without movement from among the total number of live adult scabies mites recorded at Baseline.

The proportion of adult mites with and without peristalsis respectively will be calculated at each RCM time point as the total number of adult scabies mites with and without

peristalsis from among the total number of live adult scabies mites recorded at Baseline.

A summary will present for each dose group and RCM time point: the total number and percentage of lesions assessed across all subjects, the total number and percentage of adult scabies mites with each possible morphology response (intact/not intact/unsure), and the total number and percentage of adult scabies mites with/without movement and with/without peristalsis respectively. The denominator for all percentages will be the total number of live adult scabies mites recorded at Baseline across all subjects. The number of subjects with at least one missing or incomplete lesion assessment at each RCM time point will also be summarized, as well as the number of subjects who have been administered rescue medication prior to each respective RCM time point.

There will be no imputation of missing or inconsistent data prior to the summary of the morphology, movement and peristalsis responses. Missing responses (due to the subject missing the complete RCM assessment or missing the individual lesion assessment) will be included under a 'Missing' category for each respective summary. Where an adult mite is recorded as no longer present or where a lesion is recorded as no longer visible, responses will be assumed as follows: 'not intact' for morphology, 'without movement' and 'without peristalsis' for motility.

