### **6.10.3.2 Clinician Reported Scabies Signs and Symptoms**

Subjects will be assessed for the clinical signs and symptoms of scabies infestation at Baseline, Day 7, 14 and 28. The following exploratory endpoints will be assessed using this data:

- Presence and number of total mites and burrows assessed visually at Days 7, 14 and 28.
- Changes in assessment of clinician-reported scabies symptomology, including extent of symptoms on body regions assessed by the number of anatomically-defined regions affected, number of lesions and severity grading of excoriations and erythema.

The clinician reported scabies signs and symptoms endpoints will be assessed in an exploratory manner using descriptive summaries.

Summaries will be presented for the number of subjects exhibiting each of the parasitological and clinical features, as well as those with new signs and symptoms, across all regions assessed for the subject by dose group and visit. These summaries will include the number and percentage of subjects with any:

- Mites;
- Burrows;
- Any parasitological features (mites or burrows);
- Lesions;
- Nodules;
- Excoriations (overall and by grade of excoriation);
- Erythema (overall and by grade of erythema);
- Any clinical features (lesions, nodules, excoriations or erythema);
- Any parasitological or clinical features (mites, burrows, lesions, nodules, excoriations or erythema);
- New mites relative to previous visit;
- New burrows relative to previous visit;
- New lesions relative to previous visit (including 'Yes' or 'Unsure');

- Region status at post-Baseline visits ('New region', 'Region clear from previous assessment').

The denominator for all percentages will be the number of subjects in the dose group with a non-missing assessment for at least one region at the respective visit and this will also be presented in the summaries. If a region is assessed as clear from previous assessment, it will be assumed to have no parasitological or clinical features present. If a region is new compared to the previous assessment, all mites, burrows or lesions detected at that region will be assumed to be new.

In addition to the above, the number of anatomical regions affected per subject will be summarized using descriptive statistics. This summary will exclude any regions recorded as clear from previous assessment.

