#### **6.10.3.4 Clinical Cure Rate**

Clinical cure rate is defined as resolution of all scabies signs and symptoms present at Baseline, no new scabies signs and symptoms and no evidence of mites by dermoscopy.

Clinical cure rate will be assessed at Days 7, 14 and 28. At each of these visits, a subject will be considered a responder, as determined by the clinician reported scabies signs and symptoms, if region status is 'Region clear from previous assessment', for each anatomical region assessed at that visit.

For each subject, imputation of missing assessments will be applied as follows. Where the scabies signs and symptoms assessment has been completed for a visit but this includes a missing assessment for a region previously assessed at an earlier time point, the region status will be imputed using the most recent previous assessment for the respective region (last observation carried forward). However, if the scabies signs and symptoms assessment has not been completed for a visit, or the assessments for all regions previously assessed are missing, no imputation will be applied and the subject will be excluded from the denominator for clinical cure rate at that visit.

Where rescue medication has been taken (identified on the concomitant medications page of the eCRF), any assessment indicating clinical cure response subsequent to the start date of rescue medication will be ignored and the subject will be considered a non-responder. Visit responses identified at any visit prior to or on the start date of rescue medication for the subject will be unaffected.

The number and percentage of responders, together with the Clopper-Pearson 95% CI for the percentage, will be presented for each dose group at each post-Baseline visit. The denominator for all percentages will be the number of subjects with a non-missing scabies signs and symptoms assessment for the respective dose group and visit and this will also be presented in the summary.

A flag will be added to the listing of scabies signs and symptoms data to indicate subjects identified as responders at each time point.

Following review of the above summaries, additional post hoc analyses may be considered, for example sensitivity analyses repeating the above clinical cure rate summary without imputation for missing assessments or the use of rescue medication. Any post-hoc analyses to be performed will be fully defined in a SAP Addendum prior to conducting the analyses.

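### Day 28 exploratory summaries other than clinical cure have only a version that keeps post-rescue data, so they can understate dose differences if less effective doses lead to more rescue

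*SAP*

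**What the plan says.** SAP 6.10.3 makes one exception, clinical cure, and otherwise states that "data are included in all exploratory endpoint summaries irrespective of any exposure to rescue medication". The rule covers the RCM summaries (adult motility and morphology, juvenile mites, mite stages), the clinician-reported signs, and the NRS, 5-D Itch and DLQI.

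Protocol 11.2.3 sets the conditions for rescue. For subjects found, newly or persistently, to have "confirmed scabies mites by RCM on or at any time from Day 14, standard of care may be offered". It adds: "Rescue therapy may not be offered in the absence of scabies mites or based on symptomology only".

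On timing, SAP 6.10.3.2 states: "Subjects will be assessed for the clinical signs and symptoms of scabies infestation at Baseline, Day 7, 14 and 28". The patient-reported outcomes follow the same days, and the RCM schedule also has its last assessment at Day 28.

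Elsewhere the SAP neutralises rescue. For the primary endpoints, SAP 6.10.1.3 says that "any mite death occurring after the start date of rescue medication will be ignored and the mite will continue to be considered alive", while a mite that died on or before the rescue start date stays dead. For clinical cure, SAP 6.10.3.4 says that a response after the rescue start date "will be ignored and the subject will be considered a non-responder".

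The SAP does report rescue. Section 6.8.1 tabulates its use and timing by dose group to Day 28 and flags it in the listings. The adult-motility table in 6.10.3.1 adds "the number of subjects who have been administered rescue medication prior to each respective RCM time point". No such count is specified for the other exploratory tables. Further analysis of the exploratory endpoints is optional and post hoc.

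**The concern.** Rescue depends on the outcome, because a subject must have RCM-confirmed mites to be offered it. Protocol 5.2 regards the current topical and oral treatments as effective if correctly used. If a weaker dose leaves more subjects mite-positive from Day 14, more of that group can be rescued, and the other drug's effect then appears in that group's Day 28 results.

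Three consequences follow:

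- Day 28 differences between doses can look smaller than those produced by moxidectin alone, in a trial whose first objective is to identify an optimal dose.
- The adult-mite table in SAP 6.10.3.1 follows the same Baseline mites over the same denominator as the primary mortality table. A mite killed by rescue is without intact morphology in the first and alive in the second, both at Day 28.
- The row for a fall of at least 4 points at any time after Baseline (NRS, and by cross-reference 5-D Itch and DLQI) can count a subject as improved when the fall came only after rescue.

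With about 6 subjects per group, one subject is 100/6 = 16.7 percentage points, so one or two rescues can move a row visibly.

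**Working it through.** **The plan's own figures.** The documents give no rescue rate, rescue efficacy, effect size or power, so there is no figure to reproduce. The group size of about 6 (SAP section 3) is a practical choice; 3 × 6 = 18 agrees with the n in SAP 6.10.1.4.

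**Exposed visits.** Rescue can begin at Day 14. Day 7 is therefore unaffected and Day 14 essentially so. Day 28 is the scheduled efficacy visit at which post-rescue data enter.

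**Mite presence at Day 28.** All inputs below are assumptions:

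- p = share of a dose group mite-positive from Day 14, and still positive at Day 28 without rescue: 4/6 at the lower dose (pL), 1/6 at the higher (pH)
- r = share of mite-positive subjects rescued
- s = share of rescued subjects cleared by Day 28

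With post-rescue data kept, the expected mite-positive share is p(1 − r·s). With rescued subjects counted as not resolved, it stays at p, and the contrast is 4/6 − 1/6 = 50.0 points.

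Blinding makes a common r plausible. The contrast is then multiplied by (1 − r·s):

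| r | s | 1 − r·s | lower v higher dose | contrast (points) |
|---|---|---|---|---|
| 0 | any | 1.00 | 66.7% v 16.7% | 50.0 |
| 0.5 | 0.7 | 0.65 | 43.3% v 10.8% | 32.5 |
| 0.5 | 0.9 | 0.55 | 36.7% v 9.2% | 27.5 |
| 1 | 0.7 | 0.30 | 20.0% v 5.0% | 15.0 |
| 1 | 0.9 | 0.10 | 6.7% v 1.7% | 5.0 |

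**When the contrast does not shrink.** If r differs by dose, the change in the contrast is −s(pL·rL − pH·rH). It is a loss only when a larger share of the whole lower-dose group is rescued. With s = 0.9, rL = 0.25 and rH = 1, pL·rL = pH·rH = 1/6 and the contrast stays at 50. With rL = 0.2 and rH = 1 it becomes 50 + 0.9 × (16.7 − 13.3) = 53.

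**Scores, and which correction works.** Assume itch is 6 if uncured, 1 if cured and 3 after rescue, and that all 4 and 1 mite-positive subjects are rescued.

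- No rescue effect: (4×6 + 2×1)/6 = 4.33 against (1×6 + 5×1)/6 = 1.83; difference 2.5.
- All data, as in the SAP: (4×3 + 2×1)/6 = 2.33 against (1×3 + 5×1)/6 = 1.33; difference 1.0.
- Post-rescue values excluded: 2 and 5 subjects remain, all scoring 1, so 1.0 against 1.0; difference 0.
- Last value on or before rescue carried forward, if that value was 6: 4.33 against 1.83; difference 2.5.

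Exclusion removes exactly the subjects who needed rescue and does worse than the SAP's rule.

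**The case against.** The strongest reply is that this is a disclosed choice. The exploratory summaries are descriptive and show what was observed regardless of rescue. The dose question rests on the primary mite-death endpoints, which are protected. The Steering Committee is guided by mite mortality or time to death and by safety. Rescue use is tabulated by dose group. That stands: an all-data summary is a legitimate view, and the weakness is only that it is the sole pre-specified one. Any alternative would be chosen after the Day 28 unblinding.

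Four further limits stand:

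- Rescue also covers new infestation, and Protocol 8.5.1 names untreated contacts as a source. A rescued subject is not necessarily one whose Baseline mites survived.
- The primary rule does not make every rescued subject a failure, because mites dead before rescue stay dead.
- Clinician counts cover all affected body regions, whereas the primary follows 2 to 4 selected mites. A difference between those two tables is not in itself a contradiction. The direct clash is confined to the adult-mite table in 6.10.3.1.
- Protocol 5.4.3 and 11.2.2 say that symptoms can last for weeks after treatment. A rescue at Day 14 leaves about 14 days to Day 28, so lesions, itch and DLQI should respond less than mites.

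A reader might infer that low-dose groups will be rescued most and that Day 28 results will converge, even to no mites in any group. The documents do not support that. They give no rescue rate or dose-response, rescue is optional, and complete convergence needs every mite-positive subject rescued and cleared.

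**Conclusion.** The point holds as a limit on interpreting the Day 28 exploratory summaries. If subjects are rescued before Day 28, and a larger share of the group at a less effective dose, those summaries understate the dose contrast. The direction is firm for mite presence, counts and morphology, likely for burrows, and the same in principle but weaker for lesions, itch and DLQI.

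The size rests on assumed inputs. A 50-point contrast in mite presence falls to between 32.5 and 5 points over the scenarios with rescue shown, and is unchanged without rescue.

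It would be wrong to infer that the primary dose comparison or clinical cure is contaminated: SAP 6.10.1.3 and 6.10.3.4 protect both. A second, failure-coded version is worth pre-specifying because it extends a principle that the SAP already applies and needs no new data.

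**What to change.** Keep the all-data summaries. Add to SAP 6.10.3 a second version for assessments after the rescue start date:

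1. **Binary items:** count as not resolved. Mites or burrows are present, any parasitological or clinical feature is present, and a fall of at least 4 points first reached after rescue earns no credit. For adult-mite morphology and motility, apply the rule in SAP 6.10.1.3: mites alive at rescue start stay alive, and mites already dead stay dead.
2. **Counts and scores:** do not exclude post-rescue values. Carry forward the last value on or before the rescue start date, or show rescued subjects as a separate category in the severity bands.
3. **Rescue counts:** print the number rescued before the visit, by dose group, in every Day 28 exploratory efficacy table, as 6.10.3.1 already does for motility.

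The cost is SAP wording and extra rows or panels. Rescue medication is already identified on the concomitant medications eCRF page. Carried-forward values are conservative, since they allow no later improvement on moxidectin, and the table notes should say so.

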##### **6.10.3.1 RCM Assessment**

#### **Changes in Adult Mite Motility**

The presence and changes in adult mite motility (movement and peristalsis) over time will be assessed in an exploratory manner using descriptive summaries, and with the adult scabies mite as the unit of analysis.

The proportion of adult mites with and without movement respectively will be calculated at each RCM time point as the total number of adult scabies mites with and without movement from among the total number of live adult scabies mites recorded at Baseline.

The proportion of adult mites with and without peristalsis respectively will be calculated at each RCM time point as the total number of adult scabies mites with and without

peristalsis from among the total number of live adult scabies mites recorded at Baseline.

A summary will present for each dose group and RCM time point: the total number and percentage of lesions assessed across all subjects, the total number and percentage of adult scabies mites with each possible morphology response (intact/not intact/unsure), and the total number and percentage of adult scabies mites with/without movement and with/without peristalsis respectively. The denominator for all percentages will be the total number of live adult scabies mites recorded at Baseline across all subjects. The number of subjects with at least one missing or incomplete lesion assessment at each RCM time point will also be summarized, as well as the number of subjects who have been administered rescue medication prior to each respective RCM time point.

There will be no imputation of missing or inconsistent data prior to the summary of the morphology, movement and peristalsis responses. Missing responses (due to the subject missing the complete RCM assessment or missing the individual lesion assessment) will be included under a 'Missing' category for each respective summary. Where an adult mite is recorded as no longer present or where a lesion is recorded as no longer visible, responses will be assumed as follows: 'not intact' for morphology, 'without movement' and 'without peristalsis' for motility.

### **Presence, Number, Morphology and Motility of Juvenile Mites**

The presence and characteristics of juvenile mites observed over time will be assessed in an exploratory manner using descriptive summaries.

The total number of juvenile mites across all subjects, the total number and percentage of lesions across all subjects that were assessed and the total number and percentage of lesions across all subjects where any juvenile mites were observed will be presented by dose group and RCM time point. The table will also present the total number and percentage of lesions across all subjects with each of the responses to whether any juvenile mite has intact morphology (intact/not intact/unsure), as well as the total number and percentage of lesions across all subjects where any juvenile mite does/does not exhibit movement or peristalsis respectively, by dose group and RCM time point. The denominator for all percentages will be the total number of lesions identified at Baseline across all subjects.

There will be no imputation of missing or inconsistent data prior to the summary of the juvenile mite responses. Missing responses (due to the subject missing the complete RCM assessment or missing the individual lesion assessment) will be included under a 'Missing' category for each respective summary. Where juvenile mites are recorded as no longer present or where a lesion is recorded as no longer visible, responses will be assumed as follows: 'not intact' for morphology, 'without movement' and 'without peristalsis' for motility.

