## 3 SAMPLE SIZE

The sample size chosen for this study, approximately 6 subjects per dose group, was selected to be practical and an adequate sample size for full characterization of PK profile across the dose ranges studied. Sample size was not based on formal power considerations with respect to statistical hypothesis testing.

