## **6.10 Efficacy Evaluation**

### **6.10.1 Primary Endpoint**

#### **6.10.1.1 Primary Variable**

The primary efficacy endpoint of the study will be determined by the death of adult scabies mites at each post-Baseline RCM assessment, with death defined as the degradation (homogenization of internal structures and/or external anatomic structures, and increased reflectance) of the adult mite observed by RCM.

A minimum of 2 and maximum of 4 live adult scabies mites, each within its own distinct lesion, will be identified at Baseline by RCM for each subject. Only those lesions confirmed by RCM to contain a live adult scabies mite at Baseline will be recorded on the eCRF. These identified lesions will then be further assessed by RCM at Hours 4, 8, 24, 48 and 72 and Days 7, 14 and 28 for changes in mite morphology, movement and peristalsis.

For the purposes of analysis of the primary variable, only the 2, 3 or 4 individual live adult mites identified at Baseline by RCM will be evaluated at post-Baseline time points. It is not expected that juvenile mites will mature into adults within a selected lesion being evaluated for the primary endpoint. If there is evidence to suggest that this has occurred, the data will be reviewed on a case by case basis to determine how this should be handled in the analysis.

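### The juvenile-mite table scores every lesion that is no longer visible as 'not intact' and without motility, including lesions in which no juvenile was ever recorded

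*SAP*

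**What the plan says.** The rule is in SAP 6.10.3.1, under Presence, Number, Morphology and Motility of Juvenile Mites. It reads "Where juvenile mites are recorded as no longer present or where a lesion is recorded as no longer visible, responses will be assumed" and sets the responses to "not intact' for morphology, 'without movement' and 'without peristalsis' for motility". Two triggers are joined by 'or'. The first, juveniles no longer present, implies that a juvenile had been there. The second, lesion no longer visible, carries no such condition.

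On the base for the table: "The denominator for all percentages will be the total number of lesions identified at Baseline across all subjects". The only residual category is for assessments not done: "Missing responses (due to the subject missing the complete RCM assessment or missing the individual lesion assessment) will be included under a 'Missing' category". The text names no category for a lesion in which no juvenile was seen.

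Lesions enter the study on the adult mite alone. SAP 6.10.1.1 states: "Only those lesions confirmed by RCM to contain a live adult scabies mite at Baseline will be recorded on the eCRF". Neither the SAP nor the protocol requires a juvenile at Baseline.

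The same table also gives, by dose group and time point, the total juvenile count and the number of lesions with any juvenile observed.

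**The concern.** A lesion that held an adult but never a juvenile has no juvenile to lose. Under the rule as written it enters the 'not intact', 'without movement' and 'without peristalsis' rows as soon as it can no longer be seen. Those rows then combine two different things: the fate of juveniles that were observed, and the disappearance of adult lesions.

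The effect of moxidectin on life-cycle stages is an exploratory objective, and juvenile morphology and motility is a named exploratory endpoint. Protocol 5.4.2 justifies a single dose partly by expected coverage of the whole mite life cycle, including mites that hatch after dosing. A juvenile table that moves with lesion clearance could be taken as support for that argument when it is partly a by-product of scoring. If lesions clear more often at higher doses, the by-product would rise with dose, in a study meant to identify an optimal dose.

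**Working it through.** **Comparing the three rules in SAP 6.10.3.1**

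1. *Adult motility.* The same assumed responses apply when the adult is gone or the lesion is not visible. This is coherent, because every lesion held a live adult at Baseline and there was always a mite to lose.
2. *Juvenile mites.* The wording is parallel, but a lesion need never have held a juvenile.
3. *Mite stages visible by RCM.* A lesion no longer visible is taken to have no mite stage present. That is absence, not a degraded mite. This table is at subject level, so the two tables need not clash numerically, but they describe the same lesion in different terms.

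**Following one lesion.** Take a lesion with an adult at Baseline and no juvenile at any visit. While it is visible, the text gives it no category in the juvenile morphology rows, so those rows need not add up to the denominator. Once it disappears it is counted as 'not intact'. Nothing about juveniles has changed.

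**Size.** The plan gives no figure for this table, so there is none to reproduce. The inputs are:

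- Subjects per dose group: about 6 ("The sample size chosen for this study, approximately 6 subjects per dose group, was selected to be practical").
- Lesions per subject: 2 to 4 ("A minimum of 2 and maximum of 4 live adult scabies mites, each within its own distinct lesion, will be identified at Baseline by RCM").
- Lesions per dose group, L: 6 × 2 = 12 to 6 × 4 = 24.
- v, the share of lesions no longer visible at a visit: not given; assumed 25% to 75%.
- q, the share of those lesions with a juvenile recorded earlier: not given; assumed 10% to 75%, with 0% as the limiting case.

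The denominator is taken as the Baseline lesions of the dose group. The formulas are:

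- Lesions scored 'not intact' through the visibility trigger = L × v
- Of these, lesions with an earlier juvenile = L × v × q
- Of these, lesions that never held one = L × v × (1 − q)

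With L = 24 and v = 50%:

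| q (assumed) | Scored 'not intact' as written | With an earlier juvenile | Never held a juvenile |
|---|---|---|---|
| 0% | 12 (50%) | 0 (0%) | 12 (50%) |
| 10% | 12 (50%) | 1.2 (5%) | 10.8 (45%) |
| 25% | 12 (50%) | 3 (12.5%) | 9 (37.5%) |
| 50% | 12 (50%) | 6 (25%) | 6 (25%) |
| 75% | 12 (50%) | 9 (37.5%) | 3 (12.5%) |

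The percentages do not depend on L. As a share of all Baseline lesions, the misplaced part is v × (1 − q). It runs from 0.25 × 0.25 = 6.25% to 0.75 × 0.90 = 67.5%. It is zero only if no lesion disappears, or if every lesion that disappears had a juvenile earlier.

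**Between dose groups.** Suppose q = 25% in both of two groups, with v = 25% in one and 75% in the other. The visibility trigger alone gives 'not intact' in 25% and 75% of lesions, a gap of 50 points. Lesions with an earlier juvenile account for 0.25 × 0.25 = 6.25% and 0.75 × 0.25 = 18.75%, a gap of 12.5 points. The other 37.5 points come from lesions that never held a juvenile.

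**The case against.** The SAP does not call these rows kill or mortality. The unit is the lesion and the item is whether any juvenile in it has intact morphology. For a vanished lesion it is literally true that no intact or moving juvenile is seen. 'Not intact' is equated with dead only for adults, in SAP 6.10.1.3. A reader might infer that the table reports juvenile deaths that did not occur, but the documents do not support that as a description of the output. This part of the objection stands.

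The assumption also adds nothing to the intact, with-movement or with-peristalsis rows, the juvenile count or the presence rows. Those bear most directly on whether hatched mites survive. This stands too.

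The presence rows, and the listing of all RCM data promised in SAP 6.10.1.4, would help an alert reader notice a 'not intact' count larger than juveniles could explain. This stands only in part. The rows are given time point by time point, so they cannot separate lesions that once held a juvenile from those that never did. The listing can, but only by rework.

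Finally, the table shells are a separate document and may carry a footnote or a not-applicable line. That is possible, but the SAP text is explicit about the assignment, and nothing in it limits the rule.

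**Conclusion.** The point holds on the SAP text: followed exactly, the rule puts lesions with no juvenile history into the negative juvenile rows. This is worth correcting before unblinding, but its reach is limited. It touches the negative rows of one descriptive, exploratory table. The adult-mite primary endpoints, and the adult-mite measures that guide the Protocol Steering Committee, are not affected.

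The size rests on v and q, which are assumptions, and on treating them as independent. Two stronger readings are tempting. One is that the juvenile rows mostly restate adult-lesion clearance. The other is that the table will show a false dose-response in juveniles. The documents support neither as a statement of fact. The first needs a low q. The second needs lesions to clear more often at higher doses. SAP 6.10.3 also keeps data after rescue medication in this summary, so late visits could be shifted in any group. What can be said is that the rows cannot be interpreted as written, and that a dose-related artefact is possible.

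**What to change.** In the juvenile section of SAP 6.10.3.1 and in the shells:

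1. Apply the assumed 'not intact', 'without movement' and 'without peristalsis' responses only to lesions with a juvenile recorded at Baseline or at an earlier RCM time point.
2. Place every other assessed lesion with no juvenile seen, visible or not, in a separate 'no juvenile observed' category.
3. Keep all Baseline lesions as the denominator, so that the categories, with 'Missing', sum to it.
4. Optionally, show alongside the number of lesions with a juvenile ever recorded up to that time point.

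The denominator should not be restricted to lesions that ever held a juvenile. Hatching after dosing may itself depend on dose, so that restriction would compare groups on subsets defined by a post-dose observation, possibly of very few lesions.

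The cost is about two sentences, one programming condition and one extra category. No new data are needed, because mite stages are already recorded by lesion at each RCM assessment.
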